#### **For Objective 1**

##### Data collected on the eCRF once informed consent or waiver is obtained

- Serious and non-serious ADRs to DE from the time of VTE until the end of the study for a patient
- ALL serious and non-serious ADRs other than DE from time of informed consent/ waiver until the end of the study for a patient
- All AEs with fatal outcome

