#### **For Objective 2**

##### Data collected on the eCRF once informed consent is obtained

- Serious and non-serious ADRs to DE and VKA from the time of VTE until the end of the study for a patient.

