##### Data reported on the NIS AE form once informed consent is obtained

- Serious and non-serious ADRs to DE from time of VTE until the end of the study for a patient
- All AEs with fatal outcome in patients exposed to DE

All ADRs, including those persisting after study completion must be followed up until they are resolved, have been sufficiently characterized, or no further information can be obtained.

The investigator carefully assesses whether an AE constitutes an ADR using the information below.

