### Timelines for Expedited Reporting of AEs on the NIS AE form and Drug Exposure During Pregnancy

Type of Report	Timeline
All Serious ADRs associated with dabigatran etexilate (DE)	immediately within 24 hours
All AEs with fatal outcome in patients exposed to dabigatran etexilate (DE)	immediately within 24 hours
All non-serious ADRs associated with dabigatran etexilate (DE)	7 calendar days
All pregnancy monitoring forms	7 calendar days

The same timelines apply if follow-up information becomes available for the respective events. In specific occasions the Investigator could inform the Sponsor or the Sponsor's designee (i.e., the CRO) upfront via telephone. This does not replace the requirement to complete and fax the NIS AE form.

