### Information required

For each reportable adverse event, the investigator should provide the information requested on the appropriate (e)CRF pages and the NIS AE form if applicable.

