7.9 SAFETY ANALYSES

7.9.1 Adverse events

Analyses for AEs will be based on the all eligible treated patient set. The analysis of adverse events will be descriptive in nature and will be based on BI standards (see DM&SM: Handling and summarization of adverse event data for clinical trial reports and integrated summaries [6]). Adverse events will be coded with the most recent version of MedDRA. The summary of standard AE tables will be based on the AE/ SAE CRFs. According to the reporting procedures for this study, all SAEs and outcome events are to be documented on the SAE or outcome events form irrespective of causal relationship to antithrombotic treatment or any other BI drug. Non-serious AEs which are not deemed related to antithrombotic treatment or to any other BI drug should not be included in the CRF (see study protocol, Section 11.2).

For the analysis, only AEs which are considered treatment-emergent for antithrombotic treatment are included.

For analysis of adverse drug reactions (ADRs), all AEs which are related to antithrombotic therapy according to the investigators' judgment are to be included.

The following tables will be created by treatment group:

- Overall summary of ADRs.
- Frequency [N (%)] and incidence rate (per 100 patient years) of patients with ADRs (related to antithrombotic therapy).
- Frequency [N (%)] and incidence rate (per 100 patient years) of patients with ADRs (related to antithrombotic therapy) leading to discontinuation of antithrombotic treatment.
- Frequency [N (%)] and incidence rate (per 100 patient years) of patients with ADRs (related to antithrombotic therapy) leading to death.
- Frequency [N (%)] and incidence rate (per 100 patient years) of patients with Serious ADRs (related to antithrombotic therapy).
- Frequency [N (%)] and incidence rate (per 100 patient years) of patients with fatal AEs

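### Objective 2 SAP 7.9.1 rests a by-group fatal-AE table on an all-SAE collection rule that protocol 11.2 does not contain, and the protocol is unclear on which fatal AEs reach the eCRF

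*SAP*

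**What the plan says.** Section 7.9.1 of the Objective 2 SAP says that, under the study's reporting procedures, "all SAEs and outcome events are to be documented on the SAE or outcome events form irrespective of causal relationship to antithrombotic treatment" or to any other drug of the sponsor. The next sentence deals with unrelated non-serious AEs and cites protocol 11.2. On the source of the tables it says: "The summary of standard AE tables will be based on the AE/ SAE CRFs". Only treatment-emergent events are included. Six tables by treatment group follow. Five concern ADRs; the sixth is "Frequency [N (%)] and incidence rate (per 100 patient years) of patients with fatal AEs", with no limit to related events.

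Protocol 11.2 is narrower. For Objective 2 the eCRF list has a single item: "Serious and non-serious ADRs to DE and VKA from the time of VTE until the end of the study for a patient". The Objective 2 list for the NIS AE form adds "All AEs with fatal outcome in patients exposed to DE", and the expedited-reporting timelines carry the same limit to DE. Under the heading on information required, for each reportable event "the investigator should provide the information requested on the appropriate (e)CRF pages and the NIS AE form if applicable". The Objective 1 eCRF list has the item "All AEs with fatal outcome", with no limit by drug and no stated end.

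The Objective 2 flowchart (protocol Table 9.3.1:2) has a row for fatal AEs marked at all five time points for all followed patients. The footnote to that row refers to 11.2. The flowchart has no row for SAEs in general.

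**The concern.** A rate of fatal AEs by treatment group can be read as a comparison only if fatal AEs were recorded in the same way in both groups. The SAP gives a rule that would ensure this, but the protocol section cited in the same paragraph does not contain it. The one place in the Objective 2 part of 11.2 that names fatal AEs names them for one group only.

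If deaths judged unrelated to treatment entered the AE data for DE but not for VKA, the table would show a higher fatal-AE rate for DE for reasons of collection alone. It could also disagree with the all-cause mortality analysis in the same report, and nothing in the plan would explain the difference. The table is an addition by the SAP: protocol 9.7.2.3 lists ADR parameters only, including ADRs leading to death.

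**Working it through.** The documents give no fatal-AE count or rate, so there is no figure to reproduce. The check sets the collection rules side by side and asks, for each, whether a death judged unrelated to treatment would reach the AE/SAE CRF data.

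| Rule followed by the sites | Unrelated death, DE | Unrelated death, VKA | Same in both groups? |
|---|---|---|---|
| SAP 7.9.1 sentence (all SAEs) | yes | yes | yes |
| Protocol 11.2, Objective 2 eCRF list alone | no | no | yes |
| Objective 2 flowchart row as marked, or the Objective 1 eCRF item read as open-ended | yes | yes | yes |
| Protocol 11.2 with the information-required sentence read as moving events reportable on the NIS AE form onto the eCRF | yes | no | no |

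Three things follow.

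1. Capture is unequal in only one of the four rows. That row needs an inference: the limit to DE-exposed patients stands under the NIS AE form and its timelines, and the information-required sentence does not itself say which fatal AEs go on the eCRF.
2. In the second row capture is equal, but the table would hold only fatal events judged to be ADRs. It would then largely repeat the planned table of ADRs leading to death.
3. The SAP does not match its cited source in any row except the one that restates the SAP. Protocol 11.2 does not require unrelated non-fatal SAEs on the eCRF.

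Reach: of the six tables in 7.9.1 (overall ADR summary, ADRs, ADRs leading to discontinuation, ADRs leading to death, serious ADRs, fatal AEs), one depends on fatal AEs irrespective of causality, so 1 of 6. The five ADR tables are not touched, because 11.2 collects ADRs to both drugs over the same period. No table of all SAEs is planned.

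Illustration for the fourth row only, on assumed values: suppose the true fatal-AE rates are equal, capture is complete for DE, and a share f of VKA fatal AEs is captured (those judged to be ADRs). The displayed DE/VKA rate ratio is then 1/f:

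- f = 1: 1/1 = 1.0
- f = 0.75: 1/0.75 = 1.33
- f = 0.5: 1/0.5 = 2.0
- f = 0.25: 1/0.25 = 4.0

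No value of f can be taken from the documents.

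**The case against.** A consistent reading is available. The flowchart marks fatal AEs for everyone followed, and protocol 9.3.1.3 says the flowchart sets out all data points for these patients. Objective 2 patients are drawn from Objective 1 (protocol 9.5), whose eCRF item on fatal AEs has no drug limit. The DE restriction then narrows only the NIS AE form, and the defect shrinks to one missing line in the Objective 2 eCRF list. This reading is reasonable, and on it the table is sound. It does not settle the matter, because the flowchart footnote refers the reader back to the section where that line is missing.

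It is also fair that the SAP attributes its SAE rule to the study's reporting procedures, and that the citation of 11.2 closes the following sentence. The SAP therefore does state a rule; the valid complaint is that the protocol does not match it. The section is descriptive, with no hypothesis testing, and deaths are collected separately in both groups.

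A reader might infer that deaths on VKA go unrecorded, or that the table is biased against DE. The documents support neither. Deaths are classified as outcome data and vital status is sought in both groups (protocol 9.3.3), and unequal entry on the AE forms needs the single inferred reading shown above.

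A reader might also cite the Objective 1 SAP, which ties entry on the fatal-AE page to events related to a drug of the sponsor. That text governs Objective 1 only, so it is not a competing rule for this table.

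**Conclusion.** The inconsistency is real and minor. SAP 7.9.1 states a collection rule that protocol 11.2 does not contain, and one planned by-group table depends on which rule the eCRF applied. Ascertainment is equal by group if sites followed the flowchart or the Objective 2 eCRF list alone. It favours capture in DE only if the reportable deaths limited to DE were carried onto the eCRF. The effect is confined to one descriptive table out of six; its size cannot be derived from the documents and may be nil.

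The all-cause mortality outcome has its own collection and its own planned rates by group, and it is not affected. These conclusions assume that the fatal-AE table is built from the AE/SAE CRFs, as 7.9.1 says, and not from the outcome-event form.

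**What to change.** 1. Correct the SAE sentence in 7.9.1 so that it matches what protocol 11.2 and the eCRF actually collected, and state the source of the fatal-AE table. For the record, reconcile 11.2 with the flowchart. The SAP is dated 29 May 2019 and data collection was planned to end on 31 December 2018, so the protocol text can no longer change what was collected.
2. Before reporting, count by group the deaths in the all-cause mortality outcome that fall in the treatment-emergent window (including the 6-day washout of protocol 9.7.2.3), and how many of them have a fatal-AE record. The data review meeting in SAP 6.6 is a convenient place for this, although it is described there for missing values.
3. If capture is the same in both groups, keep the table. If it differs, replace the by-group rate with a listing, or derive it from the death outcome data collected in both groups. In either case add a footnote giving the collection rule.

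Deaths by cause class (protocol 9.3.3) could be tabulated by group as well, but this is optional.

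Cost: one SAP sentence, a small reconciliation by group and possibly some site queries. The downside is that the report may carry no fatal-AE rate by group based on the AE forms.

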### 9.7.2.3 Safety analyses

Statistical analysis and reporting of safety data will be descriptive in nature, will be based on BI standards, and will focus on ADRs to dabigatran etexilate or VKA. No hypothesis testing is planned.

Occurrences of ADRs will be analyzed relative to the number of patients treated as well as observed person-years (i.e., time at risk). Safety analysis will be based on the concept of treatment emergent ADRs. Patients will be analyzed according to the anticoagulation treatment received at the time of the event. If no concurrent anticoagulation treatment is administered, then events occurring within a washout period of 6 days after discontinuation of anticoagulation treatment will be assigned to the last treatment given. This washout period will also be included as time at risk for derivation of total person-years. ADRs that deteriorate under treatment will also be considered as “treatment emergent”. Events occurring prior to first intake of anticoagulation treatment prescribed at baseline, during periods without any anticoagulation treatment (excluding washout periods), or after the end of the 1 year follow-up (excluding washout periods) will not be considered treatment emergent events and will not be included in the summary tables.

The following parameters will be included in the safety analyses:

- Adverse drug reactions
- Adverse drug reactions leading to discontinuation of anticoagulation treatment
- Serious adverse drug reactions
- Adverse drug reactions leading to deaths

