6. GENERAL ANALYSIS DEFINITIONS

6.1 EXPOSURE

Patients will be analyzed in treatment groups (DE or VKA) according to the treatment that has been prescribed at the baseline visit and at hospital discharge or 14 days after the baseline visit and recorded in the Patient Status eCRF (obtained at enrolment). The start of the follow up will be defined as the initiation of each of these two treatments.

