7.8 EXPOSURE TIME

Exposure data will be summarized based on the eligible and restricted patient sets for dabigatran etexilate and VKA. Prescribed but never taken patients will be excluded from all the analyses described in this section.

The total exposure time will be calculated for each treatment group X as:

Exposure treatment X[days]=last date of treatment intake – first date of treatment intake + 1

The calculated days are converted to months (12*days/365.25) for summary tables.

In addition, total patient years will be calculated and presented:

Total patient – years treatment X[years] = \sum_{Patients} Exposure treatment X [days]/365.25.

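### The Objective 2 SAP tabulates adverse drug reactions by initial treatment group and leaves the rate denominator unstated, which conflicts with the protocol's rule of treatment at the time of the event plus a 6-day washout

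*SAP*

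**What the plan says.** Protocol Section 9.7.2.3 sets three rules for ADRs.

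- Attribution: "Patients will be analyzed according to the anticoagulation treatment received at the time of the event".
- Washout events, where no other anticoagulant is being taken: "events occurring within a washout period of 6 days after discontinuation of anticoagulation treatment will be assigned to the last treatment given".
- Person-time: "This washout period will also be included as time at risk for derivation of total person-years". Events in untreated periods outside the washout are excluded.

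The Objective 2 SAP covers the same tables in Section 7.9.1: "The following tables will be created by treatment group". The SAP's only definition of those groups is in Section 6.1: "Patients will be analyzed in treatment groups (DE or VKA) according to the treatment that has been prescribed at the baseline visit", together with the prescription at hospital discharge or 14 days. The event filter in Section 7.9.1 is "For the analysis, only AEs which are considered treatment-emergent for antithrombotic treatment are included", and the ADR tables take "all AEs which are related to antithrombotic therapy" in the investigator's judgment. Neither condition ties the event to the drug that names the group.

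The tables report rates per 100 patient-years, but Section 7.9.1 names no denominator. Section 7.8, the exposure summary, defines days on treatment as "last date of treatment intake – first date of treatment intake + 1" and sums them into total patient-years by treatment. SAP Section 4 states that there are no changes to the planned analysis.

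**The concern.** The two documents give different answers for any patient who changes drug and then has a reaction. Such reactions will be in the data. Protocol Section 9.2.4 keeps switched Objective 2 patients in follow-up, and Section 11.2 collects ADRs to both dabigatran (DE) and VKA until the patient's end of study. If the SAP is programmed as written, a DE reaction in a VKA starter can land in the VKA column, and the reverse, or be lost.

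The rates have a second problem. Without a stated denominator, the time in which events are counted and the time they are divided by need not match. The tables concerned are those for all ADRs, serious ADRs, ADRs leading to discontinuation and ADRs leading to death. They are the descriptive ADR output of a post-authorisation safety study, and readers will take each column as describing one drug.

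**Working it through.** The documents give no switch rate and no ADR rate, so there is no planned figure to reproduce. The check is a comparison of the texts, followed by sizing on assumed inputs.

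**Text comparison**

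| Element | Protocol 9.7.2.3 | Objective 2 SAP |
|---|---|---|
| Column for an ADR | Drug at the event | Initial group (7.9.1 with 6.1) |
| Stopped, no new drug | Last drug, for 6 days | Not stated in 7.9.1 |
| Treatment-emergent | Described | Used, not defined |
| Person-time | Washout included | None named in 7.9.1; 7.8 omits washout and keeps interruption days |

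**Post-switch ADRs counted under VKA.** Assumptions: equal true ADR rates on both drugs; a fraction s of VKA starters switches to DE at 0.25 years; the others are treated for 0.5 years; switchers are treated for T years in total.

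- VKA time per starter: V = 0.5(1 − s) + 0.25s
- DE time after the switch: D = s(T − 0.25)
- Overstatement factor with VKA intake time as denominator (the 7.8 formula): (V + D)/V

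| s | V | T = 0.5 | T = 1.0 |
|---|---|---|---|
| 5% | 0.4875 | 0.5000/0.4875 = 1.026 | 0.5250/0.4875 = 1.077 |
| 10% | 0.4750 | 0.5000/0.4750 = 1.053 | 0.5500/0.4750 = 1.158 |
| 15% | 0.4625 | 0.5000/0.4625 = 1.081 | 0.5750/0.4625 = 1.243 |

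The overstatement is about 3% to 8% if switchers are treated for six months in total, and 8% to 24% if they are treated for twelve. If the denominator is all anticoagulated time, the factor is (V + D)/(V + D) = 1, so there is no overstatement.

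That zero depends on equal rates. Take 300 days of anticoagulation each, a switch at day 91 and 10% switching. With 10 ADRs per 100 patient-years on VKA and 6 on DE, the VKA column shows 9.72 even with all time counted. With 6 and 10 it shows 6.28. In both cases the column moves towards the other drug.

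**Number of events.** For 2,500 VKA starters on the same 300-day and day-91 assumptions, with 10 ADRs per 100 patient-years and 5% switching: 125 × (300 − 91)/365.25 × 0.10 = 7.2 ADRs on DE in VKA starters. At 10% switching the number is 14.3. These are the events that would be misplaced or dropped.

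**Washout.** If washout events are counted but their 6 days are not, the rate rises by 6/d for d days of exposure: 6/90 = 6.7%, 6/180 = 3.3%, 6/365 = 1.6%.

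**Interruptions.** These act in the opposite direction. For a 180-day span with a 25-day gap, the 7.8 formula gives 180 days. Treated days plus a 6-day washout in the gap and another at the end give 180 − 25 + 12 = 167. The denominator is 180/167 = 1.08 times too large, which lowers the rate.

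**The case against.** The strongest defence is that the protocol still governs. SAP Section 3 says the plan is based on protocol Section 9 and assumes the reader knows it, and Section 4 declares no change. Section 7.9.1 uses the term treatment-emergent without defining it, so the protocol's meaning could be carried over. It also defers to a sponsor standard on adverse event handling that is not among the documents.

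Part of this stands. A reader might infer that the SAP positively places a DE reaction after a switch in the VKA column. It does not say so. That is the likely result of Sections 6.1 and 7.9.1 together, but a programmer could instead drop the event or apply the protocol rule.

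A reader might also infer that the SAP defines ADR person-years without the washout. It does not: Section 7.8 is an exposure summary that Section 7.9.1 never cites. Section 7.6 gives another candidate, person time at risk with censoring at last intake plus 6 days, although it is written for outcome events.

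The sizing is also open to challenge. The 8% to 24% needs initial-drug grouping, retained post-switch events, the 7.8 denominator and longer treatment in switchers, all at once. The tables count patients with an ADR, so a patient whose reaction prompted the switch may add nothing afterwards, which the linear calculation ignores. Washout and interruption effects partly offset each other.

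What does not stand is that the protocol simply fills the gap. Section 6.1 is an explicit grouping rule, not a silence. Section 7.6 carries the last-intake-plus-6-days rule over for outcome events, while Section 7.9.1 carries over nothing. Section 7.9.1 also cites protocol Section 11.2 for recording all serious adverse events whatever their cause, whereas Section 11.2 asks for ADRs and fatal adverse events. Its alignment with the protocol cannot be presumed.

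**Conclusion.** The conflict over grouping is real and undeclared: initial treatment in the SAP, treatment at the time of the event in the protocol. Followed as written, the SAP would likely credit post-switch ADRs to the initial drug or lose them, and either outcome departs from protocol Section 9.7.2.3. The unstated rate denominator is a separate gap, and the only by-treatment patient-years formula in the SAP does not match the protocol's time at risk.

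The size cannot be fixed from the documents. It runs from no distortion to the upper figures shown above, depending on the switch rate, the treatment duration of switchers and the denominator used.

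A reader might infer that the main safety comparison is compromised. The documents do not support that. The primary outcomes are bleeding and recurrent VTE, and their as-treated analyses censor at first intake of another anticoagulant or at last intake plus 6 days (protocol Section 9.7.2.1, SAP Section 7.6). The ADR tables are descriptive, with no hypothesis testing. This should be fixed, but it is not a condition for the primary analysis.

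**What to change.** In Objective 2 SAP Section 7.9.1:

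1. Tabulate ADRs by the anticoagulant received at the time of the event (DE, VKA, other).
2. Assign events within 6 days of stopping, with no new anticoagulant, to the last drug, and define treatment-emergent accordingly.
3. State the rate denominator: days on that drug plus up to 6 washout days after a stop, cut at the start of the next anticoagulant, with other untreated days excluded.
4. Keep the Section 7.8 formula for the exposure summary only.
5. If the initial-treatment grouping is wanted, show it as a labelled supplementary table.

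If the sponsor prefers initial-treatment grouping as the main display, that departure should be recorded in SAP Section 4, with the handling of post-switch events and the denominator spelled out.

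The cost is a few sentences and some programming. Treatment start and stop dates are already collected (protocol Sections 9.3.1.1 and 9.3.1.3), so no new data are needed. The drawback is that a switcher can contribute to two columns, so patient counts will not sum to the number treated; a footnote should say so.
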